10.5 Reporting Deviations from Original Statistical Plan

The principal features of the study design and of the plan for statistical analysis of the data are outlined in this protocol. Any changes in these principal features will require a protocol or an SAP amendment, which would be subject to review by the independent DSMB, the study sponsor, and the health authorities. These changes will be described in the final clinical study report as appropriate.

11. IDENTIFICATION AND ACCESS TO SOURCE DATA

11.1 Identifying Source Data

The investigator is required to keep accurate records to ensure that the conduct of the study is fully documented. The results of all clinical and laboratory evaluations will be maintained in the subject's medical records and the data will be transferred to clinical CRFs.

Safety data will be recorded on CRFs specifically designed for this purpose. All the SAEs will be reported on an SAE report form as well as on individual CRFs. All data will be reviewed periodically by the DSMB and IRB. The DSMB and/or the IRB have the authority to withdraw any subjects and/or terminate the study because of safety findings.

11.2 Permitting Access to Source Data

The investigational sites participating in this study will maintain the highest degree of confidentiality permitted for the clinical and research information obtained from the subjects in this clinical trial. Medical and research records should be maintained at each site in the strictest confidence. However, as a part of the quality assurance and legal responsibilities of an investigation, the investigational site must permit authorized representatives of the sponsor(s) and health authorities to examine (and when required by applicable law, to copy) clinical records for the purpose of quality assurance reviews, audits, and evaluations of the study safety and progress. Unless required by the laws that permit copying of records, only the coded identity associated with documents or with other subject data may be copied (and all personally identifying information must be obscured). Authorized representatives as noted above are bound to maintain the strict confidentiality of medical and research information that is linked to identified individuals. The investigational site will normally be notified before auditing visits occur.

12. QUALITY CONTROL AND QUALITY ASSURANCE

The investigator is required to keep accurate records to ensure that the conduct of the study is fully documented.

The sponsor is responsible for regularly reviewing the conduct of the trial, for verifying adherence to the protocol, and for confirming the completeness, consistency, and accuracy of all documented data.

12.1 Compliance, Access, Entry and handling of Study Data

The site PI is required to keep accurate records to ensure that the conduct of the study is fully documented, and to ensure that CRFs are completed for all subjects according to study guidelines outlined in the study protocol and database training materials.

Access to the data entry screens will be user ID and password protected. Each user will be provided with a unique personal ID and password. The investigational site participating in this study will maintain the highest degree of confidentiality permitted for the clinical and research information obtained from the subjects in this clinical trial. Medical and research records should be maintained at each site in the strictest confidence. However, as part of the quality assurance and legal responsibilities of an investigation, the investigational site must permit authorized representatives of the sponsor(s) and health authorities to examine (and when required by applicable law, to copy) clinical records for the purpose of quality assurance reviews, audits, and evaluations of the study safety and progress. Unless required by the laws that permit copying of records, only the coded identity associated with documents or with other subject data may be copied (and all personally identifying information must be obscured). Authorized representatives as noted above are bound to maintain the strict confidentiality of medical and research information that is linked to identified individuals. The investigational site will normally be notified before auditing visits occur.

All data will be entered, stored, and managed in an encrypted database supported the DCC. The results of all clinical and laboratory evaluations will be maintained in the subject's medical records and the data will be transferred from these source documents directly to the electronic study CRFs. In addition, the data will be verified by a series of computerized edit checks, and all relevant data queries will be resolved regularly. All discrepancies will be reviewed, and any resulting queries will be resolved with the site personnel and amended in the database.

13. ETHICAL CONSIDERATIONS AND COMPLIANCE WITH GOOD CLINICAL PRACTICE

13.1 Statement of Compliance

This clinical study will be conducted using cGCP, as delineated in *Guidance for Industry: E6 Good Clinical Practice Consolidated Guidance*, and according to the criteria specified in this study protocol. Before study initiation, the protocol and the informed consent documents will be reviewed and approved by an appropriate EC or IRB, and DCC, and submitted to the applicable Health Authorities. Any amendments to the protocol or to the consent materials must also be approved by the EC or IRB, and DCC and submitted to the applicable Health Authorities before they are implemented.

13.2 Informed Consent and Assent

The informed consent form is a means of providing information about the trial to a prospective subject and allows for an informed decision about participation in the study. All subjects (or their legally acceptable representative) must read, sign, and date a consent form before entering the study, taking study drug, or undergoing any study-specific procedures. Consent materials for subjects who do not speak or read English must be translated into the subject's appropriate language and back-translated into English for review by DCC.

The informed consent form must be revised whenever important new safety information is available, whenever the protocol is amended, and/or whenever any new information becomes available that may affect participation in the trial.

A copy of the informed consent form will be given to a prospective subject for review. The attending physician will review the consent and answer questions. If required by the IRB, a witness should be present for the informed consent process. The prospective subject will be told that being in the trial is voluntary and that he or she may withdraw from the study at any time, for any reason.

13.3 Privacy and Confidentiality

A subject's privacy and confidentiality will be respected throughout the study. Each subject will be assigned a unique identification number and these numbers rather than names will be used to collect, store, and report subject information.

14. PUBLICATION POLICY

Any publications of study results will adhere to the NIH Public Access Policy.

APPENDIX 1: Sequence of Events

Time points (days relative to transplant)	S C R E N	WL ¹	BL ²	D ³	D ³	W ¹	W ²	W ³	W ⁴	M ²	M ^{2½}	M ⁶	M ⁹	M ¹²	365 post-initial Tx	Year 2				730 post-initial Tx
		1	2	3	4	5	6	7	8	9	10	11	12	13	14	Y1	15	16	17	18
Visit #	1	2	3	4	5	6	7	8	9	10	11	12	13	14	Y1	15	16	17	18	Y2
Visit Windows (specified in days)	N/A	N/A	≤ 2	N/A	N/A	± 3				± 10	± 5	± 7	±14				± 90			
Informed Consent	X																			
Medical and Diabetes History	X																			
Inclusion / Exclusion	X		X																	
Retinopathy Exam	X	X-yrly																		
Radiologic Exams																				
ECG	X	X-yrly	X													X				X
Chest X-Ray ⁷	X		X																	
Abdominal US (or MRI if clinically indicated)	X					X ⁵														
Cardiac Persantine thallium or Stress echo or equivalent	X																			
General Assessments																				
Physical Exam ⁶	X	X-yrly	X ⁶	X	X	X	X	X	X	X	X	X	X	X	X	X	X	X	X	X
Review Medications ⁸	X	X	X	X	X	X	X	X	X	X	X	X	X	X	X	X	X	X	X	X
AE/Hypo. Events		X	X	X	X	X	X	X	X	X	X	X	X	X	X	X	X	X	X	X
Clarke Score	X	X-q6Mo										X			X	X				X

Time points (days relative to transplant)	S C R E E N	WL ¹	BL ²	D ^{0³}	D ₃	D ₇	W ₁	W ₂	W ₃	W ₄	M ₂	M _{2½}	M ₆	M ₉	M ₁₂	365 post-initial Tx	Year 2				730 post-initial Tx
																	M ₁₅	M ₁₈	M ₂₁	M ₂₄	
Visit #	1	2	3	4	5	6	7	8	9	10	11	12	13	14	Y1	15	16	17	18	Y2	
Visit Windows (specified in days)	N/A	N/A	≤ 2	N/A	N/A		± 3				± 10	± 5	± 7	± 14						± 90	
Local Laboratory Assessments																					
CBC w/ Diff	X	X-q6mo	X	X ¹⁰	X	X	X	X	X	X	X	X	X	X	X	X	X	X	X	X	
Comprehensive Metabolic Panel ¹¹	X	X-q6mo	X	X ¹⁰	X	X	X	X	X	X-q1mo ¹²						X	X	X	X	X	
Calcineurin levels	X	X-q6mo	X	X	X	X	X	X	X	X	X	X	X	X	X	X	X	X	X	X	
PRA by Luminex ⁴	X	X-qMo														X	X			X	X
Coagulation (PT, PTT, INR)	X		X																		
Pregnancy test (females) ¹³	X		X																		
Serology (HBV, HCV, HIV) ⁹	X	X-yrly														X	X			X	
Fasting Lipids (TG, TC, HDL, LDL)	X	X-q6mo														X	X			X	
Apolipoprotein A1 & B, C-Reactive Protein		X														X	X			X	
T-Spot TB Test (or equivalent)	X	X-yrly														X				X	
AAT Levels ²⁶ (Send out to Quest Diagnositcs)								X													
Immunoglobulin A (IgA)	X																				
Urinalysis	X																				
Blood type/HLA	X ²¹		X																		

Time points (days relative to transplant)	S C R E E N	WL ¹	BL ²	D ³ 0	D ³	D ⁷	W ¹ 14	W ² 21	W ³ 28	W ⁴	M ² 56	M ^{2 1/2} 75	M ⁶ 180	M ⁹ 270	M ¹² 365	365 post-initial Tx	Year 2				730 post-initial Tx
																M ¹⁵	M ¹⁸	M ²¹	M ²⁴		
Visit #	1	2	3	4	5	6	7	8	9	10	11	12	13	14	Y1	15	16	17	18	Y2	
Visit Windows (specified in days)	N/A	N/A	≤ 2	N/A	N/A			± 3			± 10	± 5	± 7							± 90	
(repeat test at each islet transplant)																					
Crossmatch (repeat test at each transplant) ¹⁴			X																		
Thyroid Function (TSH)	X	X-yrly																			
Fasting C-Pep	X		X				X	X								X	X	X	X	X	
First morning spot urine (albumin & creatinine)	X	X-q3mo							X		X				X	X			X	X	
HbA1c	X	X-q3mo							X	X	X	X	X	X	X	X	X	X	X	X	
Fasting & post- prandial c-peptide ¹⁵				X	X																
Glucose immediately post-transplant ¹⁶				X																	
EBV IgG	X																				
CMV IgG, CMV IgM		X-yrly															X			X	
CMV, EBV by PCR		X-yrly	X ¹⁷									X	X								
BKV by PCR (blood)	X	X-yrly	X ¹⁷																		
GFR (CKD-EPI calculated)	X																				
MMTT - 60 & 90 min	X										X	X	X	X	X	X	X	X	X	X	

Time points (days relative to transplant)	S C R E E N	WL ¹	BL ²	D ^{0³}	D ³	D ⁷	W ¹	W ²	W ³	W ⁴	M ² _{1/2}	M ⁶	M ⁹	M ¹²	365 post-initial Tx	Year 2				730 post-initial Tx	
																M ¹⁵	M ¹⁸	M ²¹	M ²⁴		
Visit #	1	2	3	4	5	6	7	8	9	10	11	12	13	14	Y1	15	16	17	18	Y2	
Visit Windows (specified in days)	N/A	N/A	≤ 2	N/A	N/A																± 90
c-peptide & glucose ¹⁸																					
FSIGT Test	X ²⁷										X				X					X	
CGMS		X-yrly									X				X	X	X	X	X	X	
Local Pathology Testing																					
Biopsy of Auxiliary Graft				X ²⁴												X ²⁵					
Mechanistic Assays																					
TAT, C3a, C-Pep ²² Quest (San Jan Cap)			X ²⁰	X ²⁰																	
Autoantibody ²³ Barbara Davis		X													X	X	X	X	X	X	
Serum AAT level (ITN)	X						X ¹⁹	X ¹⁹	X ¹⁹	X ¹⁹											
Beta Cell DNA ²³ (Yale)		X								X	X	X	X	X	X	X	X	X	X		

1: WL = Waiting List. Repeat assessments as indicated (i.e. yrly, q3mo), while the subject is on the WL.

2: BL = Baseline. Baseline window for patients is -2 days relative to transplant.

3: Day 0 is the day of islet transplant. This SOE applies to the 1st, 2nd, and 3rd islet transplant; restarting at Day 0 for each subsequent transplant.

4: After listing, draw sample monthly for crossmatch. Run PRA by Luminex every 3 months.

5: Abdominal ultrasound to be performed within 3 days post-transplant.

6: Cardiovascular history and physical to be conducted at BL, Y1, Y2, Y3, in addition to patient physical.

7: Chest x-ray report and films will be accepted if taken within one month prior to screening. Baseline report and films will be accepted if taken within one year of Day 0.

8: At screening, review medications. Review changes at subsequent visits.

9: Serology includes: HBc Ab, HBs Ab, HBs Ag, HCV Ab, and HIV. Do not repeat Hep B tests if HBs Ab was previously positive.

10: Test repeated Days -1, 0, +1, +2.

11: Comprehensive Metabolic Panel includes: Na⁺, albumin, Mg²⁺, Cl⁻, K⁺, alk phosphatase, total bilirubin, CO₂, creatinine, ALT(SGPT), BUN, gamma GT, glucose, ST (SGOT), Ca²⁺, phosphorus.

12: Visit window for monthly labs is +/- 10 days.

13: Complete urine or serum pregnancy at screening. Complete serum pregnancy test within 72 hours prior to transplant. If urine tests positive at anytime, confirm by serum pregnancy.

14: Sample used for crossmatch may be obtained up to 30 days prior to the start of induction therapy, as long as there is no evidence of infections or transfusions since the time the sample was drawn. Crossmatch should be repeated for subsequent islet transplants.

15: C-peptide should be drawn fasting, and twice between 1-3 hrs post-prandial on Day 3 and Day 7 post-transplant.

16: Finger stick glucose should be drawn every hour for the first 6 hours immediately post-transplant.

17: CMV, EBV, and BKV by PCR immediately prior to the transplant. Post-transplant testing may be more frequent per standard of care.

18: MMTT can be done as necessary when determining islet graft failure.

19: Drawn daily during hospitalization and prior to each AAT dose.

20: TAT, C3a, & c-peptide: pre-induction AND pre transplant, 15, 30, 60, 120 min post-tx.

21: At screening, may use results from kidney transplant.

22: Serum frozen and batch shipped after each transplant.

23: Serum frozen and batch shipped at end of study.

24: Biopsy of auxiliary graft with subsequent transplants only

25: To be done in the event of graft failure for patients who do not receive subsequent transplants

26: Drawn and shipped in real time to Quest Diagnostics between 2nd and 3rd dose of AAT

27: A baseline FSIGT Test will be optional

APPENDIX 2: Reduced Follow-up Schedule of Events

Subjects prematurely discontinued from study treatment according to the criteria previously stated will remain in the study until normal termination. For the purpose of monitoring safety and efficacy parameters, the subjects should be followed according to the reduced follow-up schedule. The day on which the study treatment is discontinued is considered "Day 0". The last reduced follow-up visit will vary depending on when the subject discontinues study treatment and should be done at 3 years after the subject's final transplant.

Days post-discontinuation of study treatment	28	56	75	180	270	365	1 year post- final	2 years post- final	3 years post- final
Visit Windows (specified in days)	± 7						± 14		
Equivalent Month	1	2	2.5	6	9	12	Varies	Varies	Varies
ASSESSMENTS FOR ALL SUBJECTS ON REDUCED FOLLOW-UP									
Assess SAEs and hypoglycemic events ¹	X	X	X	X	X	X	X	X	X
Alloantibody (central)				X			X	X	X
HbA1c (central)							X	X	X
SCr (central)							X	X	X
QOL questionnaires via mail							X	X	X

1: If subject does not come to the study site for the visit, attempt to obtain information via a phone contact.

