4.1.2 Secondary Endpoints

Key Secondary Endpoint

Insulin independence

- The proportion of GLASSIA treated versus control CIT-06 subjects who are insulin independent after 1 or more islet infusions at:
 - 1 year after the first islet infusion
 - 1 year after the last islet infusion
 - 2 years after the first islet infusion
 - 2 years after the last islet infusion

Other Secondary Endpoints

Insulin Utilization

- The proportion of GLASSIA treated versus control CIT-06 subjects who are insulin independent after 1 or more islet infusions at:
 - 1 year after the first islet infusion
 - 1 year after the last islet infusion
 - 2 years after the first islet infusion
 - 2 years after the last islet infusion
- Percent change from baseline insulin requirement comparing GLASSIA treated versus control CIT-06 subjects at Day 75, 1 year and 2 years following the first and last islet transplant(s)

Islet Mass

The relative functional engrafted islet mass comparing GLASSIA treated versus control CIT-06 subjects using FSIGT testing at:

- Day 75 after the first islet transplant
- 1 year after the first islet transplant
- 2 years after the first islet transplant
- Correlation of markers of early islet loss as assessed by the rapid release of thrombin-anti thrombin complexes (TAT), C3 and c-peptide, and insulin specific DNA with FSIGT and clinical markers of islet function (HbA1c, insulin independence rates, duration of islet function and insulin independence)
- The proportion of GLASSIA treated versus CIT-06 control subjects with both an HbA1c ≤ 6.5% AND an absence of severe hypoglycemic events:
 - From Day 28 to Day 365 after the first islet transplant
 - From Day 28 to Day 730 after the first islet transplant.
- The proportion of GLASSIA treated versus control subjects with both an HbA1c < 7.0% AND free of severe hypoglycemic events:
 - From Day 28 to Day 365 after the first islet transplant.
 - From Day 28 to Day 730 after the first islet transplant
- The proportion of GLASSIA treated versus control CIT-06 subjects A reduction in HbA1c of 1 point AND an absence of severe hypoglycemia from:
 - From Day 28 to Day 365 after the first islet transplant
 - From Day 28 to Day 730 after the first islet transplant
- Number of severe hypoglycemic events comparing GLASSIA treated versus control CIT-06

subjects at 1 year and 2 years following the *first* and *last* islet transplant(s)

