5.8.3 Premature Discontinuation of Study Treatment (Transition to “Reduced Follow- up” Treatment)

Study treatment will begin at the time of the first dose of induction antibody therapy for an islet transplant. Study treatment may be prematurely discontinued for any subject for any of the following reasons:

- The subject is unwilling or unable to comply with the protocol.
- The investigator believes that the study treatment is no longer in the best interest of the subject.
- The renal allograft is lost and the subject elects to terminate chronic immunosuppression.
- Graft Failure: See Study Definitions and Section 5.8.2.
- An unexpected related SAE. The agent(s) to which the event is attributed will be discontinued.

Subjects who prematurely discontinue study treatment will remain in the study until normal termination, for the purpose of monitoring safety and efficacy parameters and will enter the reduced follow-up schedule outlined in Appendix 2. Data from these subjects will be used in the intent-to-treat analysis.

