7.6.1 Second Islet Transplant Criteria

Islet transplant recipients with partial islet graft function (see Study Definitions) will be considered for a second islet transplant in the interim between 30 ± 3 days and 8 months post-initial infusion.

Islet transplant recipients with graft failure will be considered for a second islet transplant before 8 months post-initial infusion. Please refer to the MOP for details on this process, which includes review of the potency testing from the first transplant product and post-transplant clinical data.

In order to be eligible for a second islet transplant, the following requirements must be met:

1. Subject received \leq 5,000 IEq/kg with the first transplant, but failed to achieve or maintain insulin independence.
2. Subject has been compliant with study monitoring and prescribed immunosuppressive therapy.
3. No evidence of a serious and life-threatening infection, AE, or other condition that precludes attempting an intraportal injection or continuation of the post-transplant treatment regimen.
4. Subject has no unresolved SAEs.
5. No evidence of PTLD, requiring complete withdrawal from immunosuppressive therapy.
6. No evidence of hypersensitization, allergic responses, or other potentially serious drug reactions to medications required by the protocol.
7. Stable renal function as defined as being a creatinine of no more than one third greater than the average creatinine determination performed in the 3 previous months, until rejection, obstruction or infection is ruled out.
8. Absence of any medical condition that, in the opinion of the investigator, will interfere with a safe and successful second islet transplant.
9. Absence of anti-HLA antibodies directed to the kidney transplant or to the current islet preparation detected by Luminex Single Antigen/specificity bead assay (including weakly reactive antibodies that would not be detected by a flow cross-match). All kidney and currently-proposed islet preparation donor specificities must be avoided in 2nd and 3rd islet transplants.

If graft failure occurs after the second islet transplant, these recipients will be considered treatment failures and immunosuppression will be withdrawn.

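### Reduced follow-up schedules no HbA1c at days 365 and 730 after the first transplant, so re-transplanted subjects who enter it early lack a component of the HbA1c/hypoglycaemia composites

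*Combined protocol and SAP*

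**What the plan says.** **Endpoints.** Section 4.1.2 defines three composites of an HbA1c criterion and freedom from severe hypoglycaemia, each over two periods: "From Day 28 to Day 365 after the first islet transplant" and "From Day 28 to Day 730 after the first islet transplant". It also compares HbA1c at 1 and 2 years after the first transplant, and the per-centre favourable-outcome rate uses day 730.

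**Full schedule.** Appendix 1 restarts at each transplant. It also carries separate columns for 365 and 730 days after the initial transplant, with HbA1c marked.

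**Reduced schedule.** In Appendix 2, "The day on which the study treatment is discontinued is considered" Day 0, and the columns from day 28 to day 365 count from there. None of them has HbA1c. HbA1c is marked only at 1, 2 and 3 years post-final. On where follow-up ends, the appendix says "The last reduced follow-up visit will vary depending on when the subject discontinues study treatment" and that this visit "should be done at 3 years after the subject's final transplant". There is no post-initial column. Hypoglycaemic events are assessed at every visit.

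**Who enters it.** Section 5.8.3 sends subjects who discontinue study treatment to Appendix 2. Section 5.8.2 adds subjects with graft failure once it is settled that they will have no further transplant. Section 7.6 adds those not meeting the criteria for another transplant. Section 5.8.3 also states: "Data from these subjects will be used in the intent-to-treat analysis".

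**The concern.** The endpoint clock starts at the first transplant, while the HbA1c clock in Appendix 2 starts at the final one. They agree only when there has been one transplant. For a re-transplanted subject who moves to Appendix 2 early enough, following the plan exactly leaves the endpoint-date HbA1c undrawn.

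This group is not a random subset. Graft failure with no further transplant is a main route into Appendix 2, so absence of the HbA1c is likely to be linked to a poor outcome. The plan assigns these subjects' data to the intent-to-treat analysis, yet section 10.1.2 has no rule for a composite with a missing component. The study is open-label with an external control, so a rule chosen after the data are seen would be hard to defend. A missed HbA1c cannot be recovered later.

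**Working it through.** The plan states no figure for this point, so there is none to reproduce. The check is calendar arithmetic.

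**Inputs**
- Re-transplant day *d* after the first infusion: from 30 ± 3 days to 8 months (section 7.6.1), so *d* runs from 27 to about 243. The 8-month limit also applies to a third transplant (section 7.6.2).
- Post-final HbA1c draws at 1 and 2 years: days *d* + 365 and *d* + 730 after the first transplant.
- Visit window ±14 days (section 7.7, and printed in Appendix 2). Appendix 1 also prints ±90, but the extracted table does not show reliably which columns it covers, so it is used as a sensitivity case.
- 20 transplanted subjects (section 10.3.1).

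**Nominal dates**

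| Re-transplant day *d* | 1-year post-final | 2-year post-final |
|---|---|---|
| 27 | 392 | 757 |
| 90 | 455 | 820 |
| 104 | 469 | 834 |
| 243 | 608 | 973 |

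**Overlap, ±14 on both visits.** The earliest in-window draw is *d* + 365 − 14 and the day-365 window closes at 365 + 14 = 379. Overlap needs *d* ≤ 28. The same inequality holds at day 730. Only a re-transplant on day 27 or 28 gives a usable value.

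**Overlap, ±90 on the post-initial visit.** Overlap needs *d* − 14 ≤ 90, so *d* ≤ 104 at the window edge, or *d* ≤ 90 at the nominal date. Later re-transplants are not covered.

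**Can the 1-year post-final draw stand in at day 730?** No. Its latest day is 608 + 14 = 622, and even a ±90 window at day 730 opens only at day 640.

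**Size.** The documents do not give the number affected. If *k* of 20 subjects cannot be classified, the gap between counting all as successes and all as failures is *k*/20: 5 points for *k* = 1, 10 for 2, 15 for 3 and 30 for 6. These values of *k* are assumptions.

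**The case against.** **Scope.** The gap does not reach every re-transplanted subject. Anyone entering reduced follow-up after day 365 has already had that HbA1c scheduled under Appendix 1, and anyone entering after day 730 has had both. This stands and limits the point to earlier entrants.

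**Exclusion.** A reader might infer that these subjects drop out of the intent-to-treat analysis and that the GLASSIA rate is thereby inflated. The documents do not say so. Sections 5.8.3 and 6.1 say the data are used, and nothing excludes a subject with a missing HbA1c. Exclusion is one possible handling among several.

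**Direction of bias.** Even under exclusion, the net effect on the comparison is open. Section 4.1 says the post-transplant monitoring was derived from CIT-06, so controls may have the same gap. As an illustration only, take the day-75 rates in section 10.3.1, since no composite rates are given: 10/20 and 4/24. Dropping 2 failures from the GLASSIA group gives 10/18 = 55.6%, up 5.6 points. Dropping 2 control failures gives 4/22 = 18.2%, for a net shift of 4.0 points. Dropping 6 control failures gives 4/18 = 22.2%, and the net shift is zero.

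**Partial cover.** One recorded severe hypoglycaemic event in the period fails a composite without any HbA1c, and these events are still collected. Section 7.6.1 also says: "If graft failure occurs after the second islet transplant, these recipients will be considered treatment failures". That label is not tied to the composites, however, and the default classification in the Study Definitions covers insulin independence only. A subject free of severe events remains unclassified.

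**Stated intent.** Section 7.5 says follow-up should take in time points relevant to the initial transplant. It points to Appendix 1, and Appendix 2 does not carry the intent through.

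**Interval wording.** The composites are phrased as periods, so an HbA1c reading on the last day is not spelled out. The dedicated Appendix 1 columns suggest it. On the looser reading the year-1 composite still gains nothing from Appendix 2: the earliest post-final draw is day 27 + 365 − 14 = 378, after the period ends. The year-2 period would contain the 1-year post-final draw, but no value near its end.

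**Stakes.** These are secondary endpoints without multiplicity adjustment, and section 10.1.3 lists most of them for descriptive analysis. That limits the priority but does not remove the gap.

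**Conclusion.** The point holds in a limited form. Re-transplanted subjects who enter reduced follow-up before day 365 or day 730 have no HbA1c scheduled at that date after the first transplant. The exceptions are re-transplants on about day 27-28, or up to about day 104 if ±90 applies. The plan does not say how their composites are classified. The HbA1c comparisons timed from the first transplant share the gap.

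The missingness is likely to be outcome-related, and excluding these subjects would bias the composite rates. Each unclassified subject is worth 5 percentage points of 20. How many there will be depends on graft failures, on discontinuations and on how widely section 7.6 is applied, none of which the documents quantify. The CIT-06 schedule is not available here, so the net bias in the comparison cannot be stated. Subjects with one transplant, subjects who enter later and the day-75 primary endpoint are unaffected. The schedule should be corrected; the trial's main conclusion does not depend on it.

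**What to change.** 1. Add two columns to Appendix 2, at 365 and 730 days after the initial transplant, with HbA1c and review of hypoglycaemic events, using the same windows as the matching Appendix 1 visits. Confirm there what those windows are. The cost is at most two routine blood draws per affected subject.
2. As a secondary step, state in section 10.1.2 that a transplanted subject still lacking the HbA1c component stays in the denominator. One option is to count the subject as not meeting the composite and report best- and worst-case bounds alongside. Handle CIT-06 subjects the same way as far as their data allow. The cost is a sentence or two, and possibly a somewhat lower reported rate if missing values are counted as failures.
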